## General Study Design

We will employ a three-arm, active-controlled, randomized crossover trial to assess the safety and efficacy of CICADAS app in adolescents with ASD, and to evaluate its potential as a stand-alone treatment, as a primer for PEERS, or as a treatment enhancer of PEERS. We will randomize adolescents with ASD (ages 11-18) to CICADAS only, PEERS + CICADAS app, or PEERS + Active Control app.

Approximately 56 participants will be consented to ensure the successful completion of 48 participants (16 participants per treatment arm). A diagnostic interview will be performed to determine eligibility. Following inclusion and enrollment, participants will complete a set of assessments prior to the intervention to establish their baseline performance. Participants will then be randomized to the CICADAS only group (Arm A), PEERS + CICADAS app group (Arm B), or PEERS + Active Control app group (Arm C) and spend up to 16 weeks engaged in their assigned intervention. After 16 weeks, a full battery of assessments will be administered. For the next 16 weeks, Arm A will continue with PEERS only and Arms B and C will receive no treatment during this period. At the end of the intervention period, a full battery of assessments will be administered a second time to evaluate changes in performance. Finally, participants will be asked to fill out an online exit survey to rate enjoyment, usability, perceived benefits, and ease of fit into schedule.

During the first intervention period, participants assigned to the CICADAS only will complete NB-SCT exercises for 16 weeks. Participants assigned to PEERS + CICADAS will engage with the CICADAS app and complete weekly 1-hour PEERS group sessions for 16 weeks. Participants assigned to receive the PEERS + Active Control will engage in the Active Control app and complete weekly 1-hour PEERS group sessions for 16 weeks. During the second intervention period, participants assigned to receive PEERS only will complete weekly 1-hour PEERS group sessions for 16 weeks. During both intervention periods, these participants may have weekly electronic check-ins with site study personnel (as needed). The CICADAS app and the Active Control app icons, design and user experience will look the same as to not unblind the participants.

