### Statistical Plan

Traditional Randomized Control Trials may not be the most effective way to test the efficacy of deeply-tailored, adaptive interventions. Instead, well-conducted, properly powered clinical trials that incorporate crossover design may be more useful in investigating how to optimize/enhance an evidence-based treatment (PEERS) with the experimental adjunct/primer (CICADAS). **Our trial defines: (1) three first stage treatment options; (2) a mid-study assessment point, (3) three second stage treatment options.**

After screening and enrollment, participants complete the full battery of assessments at baseline (Week 0). At Stage 1, **48** adolescents will be randomized to a 16 weeks of CICADAS only (Arm A) vs 16 weeks of PEERS + CICADAS (Arm B) vs 16 weeks of PEERS + Active Control. In order to reduce variance, we will employ a Stratified Permuted Block Randomization Design with strata defined by sensory processing symptoms to balance the number of individuals with SPA across each trial arm. After 16 weeks, the full battery of assessments will be administered again. Arms A, B and C will receive no contact for 16 weeks. At the end of the intervention, the full battery of assessments will be administered for a third time.

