**Measures of Social Cognitive Functioning:** We designed CICADAS to improve sensory processing abnormalities and social cognition in adolescents with ASD independently and to work in conjunction with PEERS to further enhance response to treatment. Our rationale is that many individuals are unable to process accurately information that underlies social and interpersonal cues. Thus, improving social cognition via targeted training of sensory processing abnormalities should confer an advantage to participants using CICADAS in conjunction with PEERS. The ability of CICADAS to prime the brain for PEERS will be measured through a subject-specific improvement in social cognition. Social cognitive functioning will be assessed a number of ways in order to gauge gains in social skills as well as ecological validity of the intervention. One of these measures will be the PEERS-based Test of Adolescent Social Skills Knowledge (TASSK; Laugeson & Frankel, 2006), a 22-item survey that assesses the teen's knowledge about the specific social skills taught during the intervention. The TASSK is comprised of sentence stems and two possible answers. Total scores range from 0 to 22, with higher scores reflecting greater knowledge of the taught social skills. Additionally, we will include the performance-based Dynamic Affective Recognition Evaluation (DARE) test for socioemotional abilities in the participant as well as parent-report measures (SRS-2, SSIS-RS) in our outcome a battery.

The secondary statistical analysis methodology is a linear mixed model approach. First, we will investigate in the ITT population any differences in baseline demographic, characterization, outcomes variables. Any such factors that show trend level significant differences ( $p < 0.1$ ) will be noted and used as covariates in the linear mixed model analysis. We will examine the data from each outcome measure using a linear mixed model with group and time as fixed factors, and covariates as necessary from the baseline analysis. Missing data will be handled with an iterative maximum likelihood procedure to optimally estimate model parameters. The key value for significance will be the group by time interaction factor for the model. Within-group effect sizes (Cohen's  $d$ ) will be computed using the mean change scores for quantitative outcomes (end-of-treatment minus baseline) and the change score SDs.

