With 48 participants fully evaluated, we will not have enough power to detect a treatment augmentation effect ascribable to CICADAS. However, data from this pilot trial will be used to power a pivotal RCT in Phase II, as they will allow to explore whether:

- a) the concurrent delivery of CICADAS and PEERS for 16 weeks (B1-B2) induces greater improvements sensory processing, cognition, symptom reduction, social skills and behaviors, as well as quality of life, compared to CICADAS only (A1-A2) or PEERS + Active Control (C1-C2) – *preliminary efficacy of CICADAS as a treatment enhancer for PEERS*;
- b) The concurrent delivery of CICADAS and PEERS for 16 weeks (B1-B2) induces greater improvements sensory processing, cognition, symptom reduction, social skills and behaviors, as well as quality of life, compared to the sequential delivery of CICADAS and PEERS (A1-A3) – *preliminary testing of CICADAS as enhancer vs primer*;
- c) improvements sensory processing, cognition, symptom reduction, social skills and behaviors, and quality of life induced by the concurrent delivery of CICADAS and PEERS (B1-B2) are sustained after 16 weeks of no contact (B2-B3) – *durability of augmentation effects*.

To verify these experimental hypotheses, we will conduct the analysis based on the pre-intervention (baseline) and post-intervention data. The criterion for statistical significance is  $p < 0.05$ . Results with  $p < 0.1$  will be described as trends.

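### PEERS alone can make the key test, the three-arm group-by-time interaction, significant, and the only effect size the SAP defines is within-group

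*SAP*

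**What the plan says.** SAP, Secondary Outcome - Preliminary Efficacy: each outcome is analysed with a "linear mixed model with group and time as fixed factors, and covariates as necessary from the baseline analysis". The decision rule follows: "The key value for significance will be the group by time interaction factor for the model". The same paragraph says that within-group Cohen's d "will be computed using the mean change scores for quantitative outcomes (end-of-treatment minus baseline) and the change score SDs". It defines no between-group effect size, confidence interval or model contrast.

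The SAP then lists three exploratory comparisons. Item (a) sets the baseline-to-week-16 change in Arm B against that in Arm A or Arm C. Item (b) compares concurrent with sequential delivery. Item (c) concerns durability in Arm B. The SAP concedes that 48 evaluated participants cannot give enough power for an augmentation effect, and adds that "data from this pilot trial will be used to power a pivotal RCT in Phase II".

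On the arms, the Protocol (General Study Design) states: "We will randomize adolescents with ASD (ages 11-18) to CICADAS only, PEERS + CICADAS app, or PEERS + Active Control app". On stage 2 the documents disagree. The Protocol has "For the next 16 weeks, Arm A will continue with PEERS only and Arms B and C will receive no treatment during this period", whereas the SAP (Statistical Plan) has "Arms A, B and C will receive no contact for 16 weeks".

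**The concern.** A test that is to speak for CICADAS should be near its nominal level when CICADAS is inert. This one need not be. In stage 1 Arm A differs from B and C in having no PEERS, so a PEERS effect is itself a group-by-time interaction. The Protocol's Background describes PEERS as supported by several randomised trials, and one outcome, the TASSK, tests knowledge of what PEERS teaches. Only B versus C holds PEERS constant.

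The within-group d has a related weakness. In Arm B it adds together CICADAS, PEERS, practice and maturation. Its endpoint is also unclear: under the Protocol's schedule, treatment ends at week 16 in B and C but at week 32 in A.

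Two things are at stake. A PEERS effect could be reported as preliminary efficacy of CICADAS, and a planning value for Phase II could be far too large.

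**Working it through.** **The plan's own figure.** The SAP gives no power and no effect size, so only the sample size can be reproduced: 56 × (1 − 0.15) = 47.6, or about 48 completers, 16 per arm (Protocol, Sample Size Justification and General Study Design).

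**Inputs.** From the documents: three arms; visits at weeks 0, 16 and 32; 16 per arm; significance at p < 0.05. Assumed, because the documents give no values: CICADAS effect zero; PEERS effect δ of 0.3, 0.5 or 0.8 baseline SD, sustained once gained; correlation ρ of 0.5 to 0.7 between any two visits; complete data.

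**Step 1: interaction test.** Degrees of freedom are (3 − 1)(3 − 1) = 4 and (48 − 3) × 2 = 90. Under the Protocol's schedule the mean profiles are A (0, 0, δ) and B = C (0, δ, δ). The interaction components are (2, −4, 2)δ/9 in A and (−1, 2, −1)δ/9 in B and in C. Their squares sum to (24 + 6 + 6)δ²/81 = 4δ²/9. Under the SAP's no-contact schedule A is (0, 0, 0) and the sum is again 4δ²/9. So λ = 16 × (4/9)δ²/(1 − ρ). For example, δ = 0.5 and ρ = 0.5 give λ = 3.56. From the noncentral F distribution:

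| PEERS effect δ | ρ = 0.5 | ρ = 0.6 | ρ = 0.7 |
|---|---|---|---|
| 0.3 SD | 12% | 14% | 17% |
| 0.5 SD | 27% | 34% | 44% |
| 0.8 SD | 64% | 75% | 88% |

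A simulation with unstructured covariance (4,000 trials per scenario) gave about 12%, 26% and 62% at ρ = 0.5, and about 17%, 43% and 85% at ρ = 0.7. The B-versus-C test of week-16 change rejected in 4-6% of trials in every scenario.

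**Step 2: practice.** With no PEERS effect and a practice gain of 0.3 or 0.6 SD per retest, equal in all arms, the interaction was significant in 4.6-5.6% of simulated trials. A common gain falls in the time main effect.

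**Step 3: within-group d.** The SD of change is √(2(1 − ρ)): 1.00 at ρ = 0.5 and 0.775 at ρ = 0.7, in baseline SD. Practice of 0.3 plus PEERS of 0.5 gives d = 0.8/1.00 = 0.80 and 0.8/0.775 = 1.03. Simulated means at 16 per arm are slightly higher, about 0.85 and 1.09, in both B and C, with CICADAS doing nothing.

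**Step 4: what a wrong planning value would do.** As an illustration, suppose B changes by 1.0 and C by 0.7 baseline SD, with ρ = 0.6. The SD of change is √0.8 = 0.894. For 80% power at two-sided 0.05, n per arm = 2 × 7.85/d². Using B's within-group d of 1.0/0.894 = 1.12 gives 13 per arm. The true contrast, 0.3/0.894 = 0.335, needs 140. The ratio is (1.0/0.3)², about 11, whatever ρ is.

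**Step 5: precision of B minus C.** The half-width is 1.96 × √(2(1 − ρ)) × √(2/16): 0.69, 0.62 and 0.54 baseline SD at ρ = 0.5, 0.6 and 0.7. Power at 16 per arm is about 13%, 29% and 62% for a difference of 0.3, 0.5 and 0.8 SD of change.

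**The case against.** These are secondary analyses in a feasibility trial. The Protocol says the sample size is not driven by hypothesis testing, the SAP admits low power, and no primary conclusion rests on this test. That stands, and it limits the harm.

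A reader might infer three stronger points that the documents do not support:

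- **That practice also drives the interaction.** It does not if it is common to all arms (step 2); it affects only the within-group d.
- **That the SAP overlooks B versus C.** Item (a) names it. However, item (a) pairs it with B versus A, where PEERS differs, under one enhancer label, and ties neither comparison to a contrast or estimate.
- **That Phase II will be sized on the within-group d.** The SAP says only that the pilot data will be used, and items (a) and (b) are between-arm comparisons. Step 4 is therefore a conditional risk.

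The size also depends on the outcome. The documents give no PEERS effect size, and nothing in them supports a large PEERS effect on the Flanker, card-sorting or SCAN-3 tests.

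Two readings would weaken the point. First, the SAP's closing paragraph refers to baseline and post-intervention data, and the Protocol calls the week-32 visit (V4) post-intervention. If only those two visits were used, the test would stay near 5% under the Protocol's schedule, but it would reject in about 13-84% of trials under the SAP's for PEERS effects of 0.3 to 0.8 SD. Second, the ITT definition requires at least one PEERS session. Combined with no contact in stage 2, that would remove Arm A and leave B versus C. Both readings rest on text that is ambiguous or contradicts the Protocol, so neither is a stated safeguard.

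**Conclusion.** The concern holds for the three-arm, three-visit interaction, which is the natural reading of the SAP. With CICADAS inert, the key value is significant in about 12-17%, 27-44% and 64-88% of trials for PEERS effects of 0.3, 0.5 and 0.8 SD. The rates are the same under either stage 2 schedule. They depend on the assumed PEERS effect and correlation; the direction does not. The within-group d cannot separate CICADAS from PEERS, practice or maturation. If it were used to plan Phase II, that trial could be much too small, but the documents do not say which effect size will be used. The primary feasibility outcomes are unaffected.

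**What to change.** In the SAP:

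- Make the key efficacy quantity the 1-df mixed-model contrast B minus C in change from week 0 to week 16, with its 95% CI.
- Add a between-arm standardised difference (that contrast divided by the pooled baseline SD) with its CI, and state that Phase II planning uses this estimate and its interval.
- Write items (b) and (c) as secondary contrasts, so that the primer and durability questions are kept.
- Keep the interaction and the within-arm d as description.
- Define end-of-treatment by week for each arm.
- Reconcile the SAP's Statistical Plan, ITT definition and list of comparisons with the Protocol on Arm A's second stage and on whether Arm A belongs to the ITT population.

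The model and the data stay the same, so the cost is a few sentences. The drawback is that the reported effect will probably be smaller, with a plainly wide interval: about ±0.62 baseline SD at correlation 0.6. That fits the SAP's own statement that power is insufficient.

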## Sample Size Justification

Attrition rates from the ASD pilot study conducted at University of Minnesota were > 30%. This high dropout rate can be ascribed to design issues, in that: (1) the sample recruited for the pilot consisted of adolescents who were not intrinsically interested in long-term treatment options for ASD, unlike the current target (adolescents already seeking PEERS); and (2) study coordinators had not been formally trained on how to keep participants engaged in a remote cognitive training intervention. By recruiting adolescents already seeking PEERS and by rigorously training our staff, we expect retention rate for this project to be in line with those of 1) cognitive interventions delivered to adolescents with ASD; 2) PEERS groups. We project a 15% non-completion rate estimate for this study. We will recruit 56 participants to obtain 48 study completers. As the primary aim of this study is to gather information about the feasibility, acceptability and usability of this approach, the sample size of N=56 is set primarily for practical reasons and not driven by hypothesis testing. This size will, however, provide data to power a subsequent pivotal efficacy trial in Phase II, and will provide the field validation data required to submit CICADAS to the FDA as a medical device for such a trial

under the 510k de novo process. We are confident that we will meet our recruitment goals with these resources in place.

Of interest to the design of our proposed trial, despite randomization to the auditory or visual training conditions, 73.2% of participants who were assigned to the Visual condition at BL completed the training whereas only 38.5% of participants who were assigned the Auditory Condition completed the program. This highlights the importance of personalized intervention programs that take individual differences (e.g., auditory sensitivity) into consideration. In fact, several participants who chose to discontinue attributed their decision to an aversion to the auditory stimuli used in the computer programs. Baseline SCAN Competing Words Test scores were significantly related to whether individuals randomized to the Auditory or Visual NB-SCT Modules completed their training [ $F(2,23) = 6.331, p = .006$ ]. In other words, participants randomized to the Auditory NB-SCT who did not complete their program had significantly more auditory processing difficulties than those who completed the program.

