#### Design and Analysis Populations

The Phase I data analysis plan *a priori* defines a primary intent-to-treat (ITT) population, a set of secondary evaluation populations, a set of primary outcome measures, a set of secondary outcome measures, five evaluation time points, a criterion for statistical significance, and a statistical analysis methodology for secondary outcomes.

There are four *a priori* defined analysis populations, including a primary analysis population (i), a secondary analysis population designed to compare effect sizes in populations with no missing data (ii), a population who completed all study visits (iii), and a population that was randomized to access CICADAS.

i. *Intent to Treat (ITT) population*: This is the *a priori* primary analysis population, defined as including all randomized participants who attended at least one PEERS session.

ii. *Intent to Treat (ITT) Fully-Evaluable (FE) population*: This is a secondary analysis population, defined as including all members of the ITT population that complete a post-intervention visit. Note that a participant may complete a specific visit but have missing data for a test in which case the participant is in the overall FE population but does not contribute data to the FE population for that visit, e.g., the number of evaluable cases for a specific test on a specific visit may be smaller than the FE population for that visit because of missing data.

iii. *Intent to Treat (ITT) Completers (C) population*: This is a secondary analysis population, defined as including all members of the ITT-FE population who complete all intervention sessions. Note that the C population is a strict subset of the FE population; a person who completes the treatment but does not complete the post-intervention evaluation visit is not a member of the C population.

iv. *Intent to Treat (ITT) CICADAS-Users (CU) population*. This is a secondary analysis population, defined as all members of the ITT population who have received CICADAS+PEERS, except those who drop/withdraw post-randomization and pre-treatment.

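### Within-group effect sizes are defined outside the mixed model's missing-data handling, so at the same visit ITT and Fully-Evaluable values are identical and cannot show the influence of missing data

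*SAP*

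**What the plan says.** **Model and test.** Under Secondary Outcome - Preliminary Efficacy, the SAP fits a linear mixed model with group and time as fixed factors. "Missing data will be handled with an iterative maximum likelihood procedure to optimally estimate model parameters". For the test, "The key value for significance will be the group by time interaction factor for the model".

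**Effect sizes.** The same paragraph then defines within-group Cohen's d values, which "will be computed using the mean change scores for quantitative outcomes (end-of-treatment minus baseline) and the change score SDs". No imputation or model-estimated change is mentioned. The SAP does not use the word observed, but that is the plain reading.

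**Populations.** Under Design and Analysis Populations, ITT is defined as "including all randomized participants who attended at least one PEERS session", and Fully-Evaluable (FE) as "including all members of the ITT population that complete a post-intervention visit". The overview in that section introduces FE as "a secondary analysis population designed to compare effect sizes in populations with no missing data (ii"). Neither the end-of-treatment point nor the post-intervention visit is tied to week 16 or week 32.

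**Use and expected loss.** The SAP states that "data from this pilot trial will be used to power a pivotal RCT in Phase II". Protocol, Sample Size Justification: "We project a 15% non-completion rate estimate for this study". That section also gives pilot attrition above 30%, and reports that pilot participants who did not complete auditory training had worse baseline auditory processing than those who did.

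**The concern.** A change score exists only for someone with both a baseline and an end-of-treatment value. An effect size built from change scores is therefore an available-case figure, whichever population label it carries. The SAP's missing-data method covers the model parameters and does not reach d.

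Two things are at stake. First, d is the only effect-size statistic that the SAP specifies, and it may describe those who were assessed rather than the ITT population named as primary. Second, the comparison of ITT with FE effect sizes will tend to reassure, because both figures leave out the people whose absence is in question.

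The pilot makes this more than theoretical. Completion was related to a baseline SCAN subtest, and SCAN-3:A is an outcome in this trial and part of the SAP's Cognition composite.

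**Working it through.** **1. The plan's own figure.** Inputs from Sample Size Justification: 48 completers, 15% non-completion, 56 recruited.
- 48 / (1 - 0.15) = 56.5, rounded up to 57; 48 x 1.15 = 55.2, rounded up to 56; 56 x 0.85 = 47.6. The stated 56 is reproduced to within one participant.
- Non-completers: 56 - 48 = 8. At the pilot's 30%: 56 x 0.30 = 16.8, about 17.
- These are the numbers without a change score only if every non-completer also misses the end-of-treatment visit.

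**2. Who enters each effect size.** Take one test at one visit.
- ITT d uses ITT members with a baseline score and a score at that visit.
- FE d, with FE defined by that visit, uses ITT members who attended it and have the same two scores.
- These are the same people. In 5,000 simulated arms of 19 (56 / 3 = 18.7), the largest difference between the two values was 7e-16, which is rounding.
- If FE means attending week 32 and d is taken at week 16, the two can differ. With an assumed 10% loss between the visits, they differed in 81% of simulated arms, by 0.07 on average. Neither figure includes anyone lost before week 16.

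**3. Size of the bias when loss depends on baseline.** The documents give no effect size, SD or correlation, so these are assumptions: baseline and follow-up SD of 1, correlation r of 0.5 or 0.7, true d of 0.5, higher scores better, and logistic loss on baseline with slope 0, 1 or 2 in either direction, set to 15% or 30% overall.

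The observed mean change equals the true mean change plus (r - 1) x (mean baseline of those observed, measured from the overall mean). Because r - 1 is negative, losing people with low baselines lowers d and losing people with high baselines raises it.

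Observed-change d from 1,000,000 simulated participants per scenario (slope 1, slope 2):

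| Loss | r | Lower baselines leave | Higher baselines leave |
|---|---|---|---|
| 15% | 0.5 | 0.438, 0.409 | 0.573, 0.617 |
| 15% | 0.7 | 0.454, 0.430 | 0.556, 0.588 |
| 30% | 0.5 | 0.379, 0.325 | 0.638, 0.714 |
| 30% | 0.7 | 0.405, 0.361 | 0.605, 0.658 |

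With random loss, observed-change d was 0.500 to 0.503. The maximum-likelihood d, using the model-implied SD of change, was 0.497 to 0.503 in every scenario.

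**4. What the likelihood estimate does not correct.** Suppose instead that completers gain 0.40, those lost gain nothing, and loss is unrelated to baseline.
- At 15% loss the true mean is 0.85 x 0.40 = 0.34. In simulation, observed change and maximum likelihood both gave 0.401.
- At 30% loss the true mean is 0.70 x 0.40 = 0.28, and both gave 0.400.

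**5. Between-arm contrasts.** If baseline-dependent loss follows the same pattern in each arm, the shift in step 3 is the same in each and cancels in the difference. For a true difference of 0.30, simulated observed-change differences were 0.297 to 0.302.

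**The case against.** The strongest reply is one of proportion. This is a feasibility trial, d is descriptive and secondary, and the hypothesis test already uses maximum likelihood. That stands: neither the primary outcomes nor the group-by-time test is affected.

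Stopping the programme is also not the same as missing the assessment. The protocol lets participants cease use and still attend V3 or V4 once a minimum is met, and the SAP puts that minimum at one hour of app use, plus one PEERS session where the arm includes PEERS. So 15% and 30% may overstate the share without a score, and it would be wrong to say that every dropout is excluded. The protocol also gives reasons why pilot attrition should not recur, and the pilot finding concerns programme completion, not missing outcome assessments.

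Finally, ITT and FE estimates from the mixed model could still be compared. That is true, but the SAP states the purpose of FE in terms of effect sizes, and the effect size it defines is the change-score d.

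What remains is a definition that leaves unassessed participants out of an ITT figure, and a planned comparison that at the same visit returns the same number twice.

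**Conclusion.** The point holds in a limited form. On the plain reading of the SAP, participants with no end-of-treatment score are outside d in every population, and at the same visit ITT d and FE d are identical. The bias is nil under random loss. Under baseline-dependent loss, with an assumed true d of 0.5, observed-change d lies between 0.41 and 0.62 at 15% loss and between 0.33 and 0.71 at 30%, and the likelihood estimate recovers 0.5. This rests on the assumed correlations and loss mechanism, and on week 0 being a response in the mixed model.

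A reader might infer that d will be inflated and Phase II underpowered as a result. The documents do not support that:
- Inflation of that kind needs those lost to have responded poorly for unobserved reasons. The pilot says nothing about the gains of non-completers, and step 4 shows that a model-based d would be equally wrong.
- If the pilot's pattern carried over to assessments, with those worse at baseline leaving, step 3 gives a d that is too low.
- The SAP says that pilot data will inform Phase II. It does not name within-group d, and the mixed model also yields between-arm estimates, in which similar loss cancels.

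One limit applies to Arm A. ITT requires a PEERS session, and on the protocol's schedule Arm A has PEERS only in the second 16 weeks, while the SAP's Statistical Plan gives that arm no contact then. On either text, an Arm A participant lost before week 16 is not in ITT at all. The argument therefore bears most directly on Arms B and C.

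**What to change.** - **SAP, Secondary Outcome - Preliminary Efficacy:** compute within-group d as the mixed-model estimated change at a named end-of-treatment week, using all ITT participants with a baseline value, divided by a stated SD, with a 95% confidence interval.
- **SAP, Design and Analysis Populations:** tie the post-intervention visit to a named week, and make the planned comparison the model-based ITT d against the observed-change FE d at that week.
- **Both documents:** reconcile the second-period schedule for Arm A, so that end of treatment has one meaning, and settle how the ITT definition applies to that arm.
- **Optional:** add a sensitivity d in which participants without an end-of-treatment score are assigned no change. This addresses loss related to poor response, which the model-based d does not.

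The cost is SAP wording and a little more analysis, with no new data or visits. The reported d may move in either direction.
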